9.4.2. Primary/Secondary Endpoints

Immunogenicity Endpoints

Descriptive statistics (geometric mean and confidence intervals, or median and interquartile range Q1-Q3, as appropriate) will be calculated for continuous immunologic parameters. Several definitions of serological response will be applied (fold increases in GMT [VNA] or GMC [ELISA]). Graphical representations of immunologic parameters will be made as applicable. Frequency tabulations will be calculated for discrete (qualitative) immunologic parameters, as applicable.

In addition, the ratio between neutralizing and binding antibodies as determined by VNA and S protein ELISA, respectively, will be calculated together with confidence intervals.

For adults, all data will be analyzed separately from the point of unblinding for safety and immunogenicity. Details will be described in the SAP.

For adolescents, limited pooled safety and reactogenicity data (planned for IDMC review) and group unblinded immunogenicity data (summary of S-ELISA, including GMC, and seroresponse rates for all participants and seronegative at baseline participants, in Ad26.COV2.S 2.5x10¹⁰ vp only) were reviewed by the sponsor prior to Amendment 6 (see Section 4.1 Overall Design).

The immunogenicity analyses will be performed on the PPI population. Immunogenicity analyses will also be done on the FAS (participants who became infected during the study will be analyzed as a subgroup and shown in the graphs using different colors and symbols).

Safety Endpoints

No formal statistical testing of safety data is planned. Safety data will be analyzed descriptively by vaccine group. In addition, for selected tables, tabulations pooled by vaccine dose will also be provided. All safety analyses will be done on the FAS.

Adverse Events

The verbatim terms used in the eCRF by investigators to identify AEs will be coded using the Medical Dictionary for Regulatory Activities (MedDRA). All reported AEs will be included in the analysis. (S)AEs caused by molecularly confirmed SARS-CoV-2 infection will be removed at the analysis level from the (S)AE listings and tables and presented separately. For each AE, the percentage of participants who experience at least one occurrence of the given event will be summarized by vaccine group.

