4. POPULATIONS (ANALYSIS SETS) FOR ANALYSIS

For vaccine studies, study intervention assignment will follow the as treated principle: all analyses (including safety, immunogenicity and efficacy analyses) will be analyzed by the actually received vaccine.

Population	Description
All screened participants (ALL)	The “all screened participants” set includes all participants that were screened, regardless of whether they were enrolled and/or randomized.
All randomized participants (ALL RANDOMIZED)	The “all randomized participants” set includes all participants that were randomized to one of the treatment groups.
Full Analyses Set (FAS)	The full analysis set will include all participants with at least one vaccine administration documented.
Per Protocol Immunogenicity Set (PPI)	The per protocol immunogenicity population will include all randomized and vaccinated participants for whom immunogenicity data are available. Samples taken after a participant meets the criteria for a major protocol deviation expected to impact the immunogenicity outcomes will be excluded from the PPI analysis. In addition, samples obtained after missed vaccinations or participants with natural infection occurring after screening (if applicable) will be excluded from the analysis set. SARS-CoV-2 infection is defined as a positive PCR test or positive N-serology.

Two additional analysis sets are defined in Appendix 2 : PPI modified and FAS modified.

The safety and COVID-19 cases analyses will be censored at the date of unblinding or the receipt of an unscheduled vaccine^a, whichever event occurs first. AEs and COVID episodes reported after unblinding or receipt of an unscheduled vaccine, whichever comes first, will be listed.

The immunogenicity analyses will be censored at the date of the receipt of

- an unscheduled vaccine,
- another live vaccine,
- unknown vaccine which is received in the window of +/-29 days at each dosing,
- other not live vaccine which is received in the window of +/-15 days at each dosing.

Immunogenicity samples excluded for the above reasons will be included in the listings and flagged.

^a Unscheduled vaccine: an authorized/licensed COVID-19 vaccine offered outside of the study.

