Safety analyses will be performed on the FAS. Continuous variables will be summarized using the following statistics, as appropriate: number of observations, arithmetic mean (mean), standard deviation (SD), standard error (SE), median, quartiles (Q1 and Q3), minimum and maximum. Frequencies and percentages (one decimal place) will be generated for categorical variables. No formal comparisons between groups will be provided.

Safety data will be analyzed by study intervention regimens as designed per protocol^a. In addition, safety data will be analyzed by intervention regimens as designed per protocol and age group. Data will be presented by period (post Dose 1, post Dose 2, post Antigen Presentation, as applicable) as well as over the entire primary regimen, and over the entire Antigen Presentation regimen. Denominator for the percentages is the number of participants in the considered population and phase for a certain regimen (incidence per 100 participants/phase).

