5.6.1. Adverse Events

5.6.1.1. Definitions

Solicited AEs shown in the tables are extracted from the investigator assessment pages (CE) of the CRF. For unsolicited AEs, only the AEs within the 28-day period following each vaccination will be presented in the safety tables except for SAEs, which will be captured and tabulated in the outputs covering the whole study period. All other collected unsolicited adverse events will be presented through listings.

Solicited administration site symptoms will be considered as related to the study vaccine (by definition).

The severity of the AEs will be classified as grade 1 to 4. Solicited events that are graded less than grade 1, are not considered as AE. In case no grades are available, the grading of the solicited events will occur according to the grading list in Appendix 3.

For AESI, the following is defined:

- Suspected AESI : as reported by investigator and presented by: Embolic and thrombotic events (SMQ) + PT; Haematopoietic thrombocytopenias (SMQ) (broad) or HLT Thrombocytopenias + PT; Other SMQ + PT.
- Suspected AESI: Embolic and thrombotic events (SMQ), Haematopoietic thrombocytopenias (SMQ) (broad) or HLT Thrombocytopenias and presented by: Embolic and thrombotic events (SMQ) + sub-SMQ1 + PT; Haematopoietic thrombocytopenias (SMQ) (broad) or HLT Thrombocytopenias + PT;
- Qualified for assessment AESI: [Embolic and thrombotic events (SMQ)] and [Haematopoietic thrombocytopenias (SMQ) (broad) or HLT Thrombocytopenias or platelet count below normal ranges per local or central laboratory report or platelet count < 150 × 10⁹/L] and presented by: Embolic and thrombotic events (SMQ) + sub-SMQ1 + PT;

^a As indicated previously, all analyses, including the safety analyses, will be conducted by actually received vaccine (“as treated” principle). The sentence “by study intervention regimens as designed per protocol” indicates that the statistical tables are designed with the planned vaccine regimens as columns. Therefore, participants who receive e.g. “Placebo, Placebo” instead of “Ad26.COV2.S 5x10¹⁰ vp, Placebo” will appear in the “Placebo, Placebo” column. However, to avoid sparse columns, participants who receive e.g. “Placebo, Ad26.COV2.S 5x10¹⁰ vp” (which is not a planned vaccine regimen) will be excluded from the statistical tables. They will be included in the listings, as well as in the programmed patient narratives where they will appear as “Subjects with vaccine misallocation”.

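### The SAP leaves vaccinated participants with an unplanned injection sequence out of the regimen-column safety tables, so those tables cover a subset of the FAS, and Appendix 2 does not declare it

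*SAP*

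**What the plan says.** Protocol 9.4.2 fixes the safety population: "All safety analyses will be done on the FAS". SAP 4 defines that set in the same words as Protocol 9.3: "The full analysis set will include all participants with at least one vaccine administration documented". Neither definition depends on which sequence of injections was received. SAP 5.6 repeats the commitment: "Safety analyses will be performed on the FAS".

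SAP 4 also sets an as-treated rule, under which "all analyses (including safety, immunogenicity and efficacy analyses) will be analyzed by the actually received vaccine". A footnote to SAP 5.6, printed with 5.6.1.1, explains how this works in tables whose columns are the planned regimens. A misallocated participant whose received sequence equals another planned regimen moves to that regimen's column. For the remainder, the sentence begins "However, to avoid sparse columns, participants who receive e.g", gives as its example placebo followed by 5×10^10 vp, and ends "which is not a planned vaccine regimen) will be excluded from the statistical tables". The next sentence says where they do appear: "They will be included in the listings, as well as in the programmed patient narratives where they will appear as" subjects with vaccine misallocation.

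The table denominator in SAP 5.6 is specific to the regimen: "Denominator for the percentages is the number of participants in the considered population and phase for a certain regimen".

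**The concern.** The people affected have been vaccinated, so they belong to the FAS by definition. The footnote does not change who is in the FAS. It changes who is counted in the tables, and it does so for a layout reason. It makes no exception for SAE or AESI tables, although solicited and unsolicited AEs, SAEs and AESIs are primary endpoints for adults (SAP 5.3).

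An adverse event in such a participant would be absent from the tabulated incidences. Because the denominator is specific to the regimen, the participant leaves the numerator and the denominator together, so the printed percentage gives no sign that anyone is missing. A reader who relies on the statement that safety is analysed on the FAS would take the table as complete.

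**Working it through.** **1. Comparing the texts.**

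| Source | Who is in the safety tables |
|---|---|
| Protocol 9.3 and 9.4.2 | All with at least one documented vaccination |
| SAP 4 and SAP 5.6 main text | The same |
| SAP 5.6 footnote | The same, minus those whose received sequence is no planned regimen |
| SAP Appendix 2 | Silent on the footnote's exclusion |

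Appendix 2 is the section for declaring such departures. It declares a different one: the 2 participants given Vaccination 2 at 28 days before the study pause are shown only in listings for safety. The footnote's rule has no matching entry.

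**2. The plan's own precision figure.** Protocol 9.2.2, Table 9, gives the one-sided 95% upper limit on an event rate when no events are seen. The formula is 1 − 0.05^(1/N).

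| N | Recomputed | Table 9 |
|---|---|---|
| 25 | 11.29% | 11.3% |
| 50 | 5.82% | 5.8% |
| 75 | 3.92% | 3.9% |
| 150 | 1.98% | 2.0% |

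Table 9 reproduces.

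**3. Effect on precision.** The documents give no count of misallocations, so take k = 1 to 5 dropped from one group as an assumption and use 1 − 0.05^(1/(N − k)).

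| N | k = 0 | k = 1 | k = 5 |
|---|---|---|---|
| 75 | 3.92% | 3.97% | 4.19% |
| 50 | 5.82% | 5.93% | 6.44% |
| 25 | 11.29% | 11.73% | 13.91% |

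This effect is small, and at k = 0 there is none.

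**4. Effect of a lost event.** Suppose one randomised participant is dropped and had the group's only event. The limits are exact one-sided 95% upper limits.

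| Randomised group | Event counted | Upper limit | Event dropped | Upper limit |
|---|---|---|---|---|
| 75 | 1/75 = 1.33% | 6.17% | 0/74 = 0% | 3.97% |
| 50 | 1/50 = 2.0% | 9.14% | 0/49 = 0% | 5.93% |
| 25 | 1/25 = 4.0% | 17.61% | 0/24 = 0% | 11.73% |

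**5. Share of the study.** Of 550 planned adults, 1 dropped is 1/550 = 0.18% and 5 dropped is 5/550 = 0.91%.

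**The case against.** The strongest reply is that the rule is narrow and openly stated. Only sequences matching no planned regimen are affected. The participants remain in the listings and in labelled narratives, and SAP 5.6.1.2 provides listings or narratives, as appropriate, for deaths, vaccination discontinued because of an AE, and severe or serious AEs. A reader might infer that such an SAE could disappear from the report. The documents do not support that: it would be reported individually, though not tabulated.

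A reader might also infer that the footnote contradicts the as-treated principle. It does not. It applies the principle where a matching column exists and stops where none does, so the principle is incompletely applied. Nobody is tabulated under the wrong vaccine.

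Nor do the documents say that every safety display drops these participants. The footnote concerns tables with planned regimens as columns. Protocol 9.4.2 also promises selected tables pooled by vaccine dose, and the SAP does not say how those treat the participants. Exclusion from them is an inference.

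The obvious remedy, placing each participant in every period under the injection received, also has a fault. A first injection of 5×10^10 vp fits Groups 1, 5, 7 and 9, and a first placebo fits Groups 6, 8 and 10 (Protocol 4.1, Table 2), so one injection need not identify one column. In the footnote's own example the second injection is a first active exposure, and placing it in Group 1's post-dose 2 column would mix it with second active exposures.

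Finally, the study is descriptive, safety tables show frequencies and percentages without formal comparison, and the upper limits above are not planned outputs.

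All of this stands, and it limits the weight of the point. It does not reconcile the footnote with the statement that safety analyses are on the FAS, because a listing does not enter a tabulated incidence.

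**Conclusion.** The point holds for the regimen-column safety tables. As written, they are on the FAS minus participants with an unplanned received sequence, contrary to Protocol 9.4.2 and to the main text of SAP 5.6, and the departure is not declared in Appendix 2. Its numerical size is unknown and may be nil. If a few participants are affected, the precision cost is slight. The real exposure is a tabulated zero where the randomised group had one event, such as 0/74 in place of 1/75. That illustration assumes at least one such misallocation and that this participant had the group's only event. It supports neither a claim that safety data are lost from the report nor a claim that all safety displays are affected. The remedy is cheap and the endpoint is primary, so the change is worth making. SAP 5.7.1 carries a similar footnote for immunogenicity, which this point does not cover.

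**What to change.** Amend the SAP 5.6 footnote as follows:

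- Keep participants with an unplanned received sequence out of the planned-regimen columns. In particular, do not place them in a planned regimen's post-dose 2 column.
- Count them in the safety tables, including the SAE and AESI tables, in a single 'other sequence' column.
- By period, also count them in an overall total, or in an 'any Ad26.COV2.S' total from their first active injection onward.
- State the number affected in a table footnote.

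If the sponsor prefers to keep the exclusion, the minimum is to declare it in Appendix 2 and give the number excluded with their AE and SAE counts.

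The cost is one extra sparse column or total and minor programming. The planned-regimen columns do not change.

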5.6.1.2. Analysis of Adverse Events

Number and percentage of participants with at least one particular AE (unsolicited/solicited) will be tabulated. Unsolicited AEs will be summarized by System Organ Class and Preferred Term. Solicited AEs will be summarized by class (administration site/systemic) and Preferred Term.

For solicited AEs following tables will be provided: summary, by worst severity grade, at least grade 3, related (systemic only), time to onset (in days) and duration (in days) for most frequent events and body temperature. Note: Duration is defined as number of days from the start of the event until resolution of the event. The time to first onset is defined as (date of first onset – reference date + 1). The reference date is the start date of the vaccination period.

For unsolicited AEs, the following tables will be provided: summary table (including SAE, fatal outcome, and discontinuation), all events, most frequent, at least grade 3, permanent stop of vaccine, related, and SAE.

As a general remark, COVID-19 cases will be analyzed separately (see section 5.7.3).

- SAEs that are COVID-19 related will not be included in the SAE tables, but will be included and flagged in the SAE listings. In MedDRA version 23.0, Preferred Terms (PT codes) “COVID-19 (10084268)”, “COVID-19 pneumonia (10084380)”, “Suspected COVID-19” (10084451), and “Asymptomatic COVID-19 (10084459)”, “Coronavirus infection” (10051905), “Severe acute respiratory syndrome” (10061982), “SARS-CoV-2 carrier” (10084461), “Exposure to SARS-CoV-2” (10084456) and “Occupational exposure to SARS-CoV-2” (10084394) will be considered COVID-19 related AEs^a.

Listings and/or participant narratives will be provided as appropriate, for those participants who die, discontinue study vaccinations due to an AE, or experience a severe or serious AE.

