10.4.1. Adverse Event Definitions and Classifications

Adverse Event

An AE is any untoward medical occurrence in a clinical study participant administered a pharmaceutical (investigational or non-investigational) product. An AE does not necessarily have a causal relationship with the vaccine. An AE can therefore be any unfavorable and unintended sign (including an abnormal finding), symptom, or disease temporally associated with the use of a medicinal (investigational or non-investigational) product, whether or not related to that medicinal (investigational or non-investigational) product. (Definition per ICH)

This includes any occurrence that is new in onset or aggravated in severity or frequency from the baseline condition, or abnormal results of diagnostic procedures, including laboratory test abnormalities.

Any respiratory tract infection will be reported as an AE if it occurs between the time of any vaccination through the following 28 days. Any respiratory tract infection recorded as an AE in the eCRF will be excluded from any AE analysis if the molecular test is subsequently found to be positive for SARS-CoV-2. Respiratory tract infections arising from SARS-CoV-2 infection will not be reported as (S)AEs in the Clinical Study Report but will be tabulated separately. In general, (S)AEs caused by molecularly confirmed SARS-CoV-2 infection will be removed at the analysis level from the (S)AE listings and tables and presented separately.

Note: For time period of sponsor's AE collection, see All Adverse Events under Section 8.3.1, Time Period and Frequency for Collecting Adverse Event and Serious Adverse Event Information.

Serious Adverse Event

An SAE based on ICH and EU Guidelines on Pharmacovigilance for Medicinal Products for Human Use is any untoward medical occurrence that at any dose:

- Results in death
- Is life-threatening (The participant was at risk of death at the time of the event. It does not refer to an event that hypothetically might have caused death if it were more severe.)
- Requires inpatient hospitalization or prolongation of existing hospitalization
- Results in persistent or significant disability/incapacity
- Is a congenital anomaly/birth defect
- Is a suspected transmission of any infectious agent via a medicinal product

Is Medically Important*

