5.7.3. COVID-19-like Signs and Symptoms

Procedures to be performed in the event a participant experiences signs or symptoms suggesting possible COVID-19 are detailed in CTP Sections 1.3 Schedule of Activities and 8.1.2 Procedures in case of COVID-19-like Signs and Symptoms.

The presence of SARS-CoV-2 infection will be assessed at the study site by molecular testing using the nasal swab sample.

The following analyses will use the FAS set and will be conducted at the time of the final analysis:

The number and percentage of participants with at least one molecularly confirmed SARS-CoV-2 infection will be tabulated by vaccine regimen, for the entire study period only.

The number and percentage of participants with at least one positive non-S protein ELISA (e.g., N ELISA), if available, will be tabulated by vaccine regimen. The analysis will be repeated pooling all active regimens vs. placebo, where data from all cohorts will be pooled.

For each participant with confirmed COVID-19 infection, a narrative will be prepared based on the visit performed 28 days after the onset of COVID-19 signs and symptoms and other selected information from the clinical database, as available:

- participant ID
- vaccination regimen
- sex, race, ethnicity, age, BMI, dates at which vaccinations were received
- pulse oximetry
- physical examination findings based on the visit performed 28 days after the onset of COVID-19 signs and symptoms
- vital signs including body temperature based on the visit performed 28 days after the onset of COVID-19 signs and symptoms
- Humoral immune responses as collected at the planned time points + those obtained from the blood sample taken on the visits performed 3 and 28 days after the onset of COVID-19 signs and symptoms. This information may be presented graphically.

For the analysis of the SIC (Patient Reported Outcomes, PRO) data, the following considerations apply

- An “episode” is defined as a period in which any symptoms are reported on the SIC, starting from the first day on which symptoms were reported until the first day that the PRO was not completed because the symptoms had resolved (this will be indicated in the

SDTM data, with reason for not completing the PRO = “Symptoms resolved” (or similar) or death

- A symptom (e.g. feeling generally unwell, fatigue, physical weakness, cough, etc.) is assumed to be present on each day the associated Yes/No question is answered “Yes” or the associated severity question has a rating > 0.

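### SAP 5.6.1.2 drops SAEs from the SAE tables by preferred term, confirmed or not, whereas the protocol removes only events caused by molecularly confirmed infection

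*SAP*

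**What the plan says.** SAP 5.6.1.2 sets the rule: "SAEs that are COVID-19 related will not be included in the SAE tables". The same sentence keeps these events in the SAE listings, with a flag. It then names nine MedDRA preferred terms that "will be considered COVID-19 related AEs". The list mixes terms for infection with "Suspected COVID-19" and two terms for exposure (general and occupational). No term is made conditional on a test result. A footnote lets the Data Presentation Specifications revise the list. The section refers to SAP 5.7.3 for the separate analysis of COVID-19 cases.

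The protocol's rule is different. Section 9.4.2 says that (S)AEs "caused by molecularly confirmed SARS-CoV-2 infection will be removed at the analysis level from the (S)AE listings and tables and presented separately". Section 10.4.1 repeats this and adds rules for respiratory tract infections. Such an event recorded as an AE "will be excluded from any AE analysis if the molecular test is subsequently found to be positive for SARS-CoV-2". A respiratory event that meets the SAE criteria is an SAE if testing shows it is not SARS-CoV-2. If no result is available within 24 hours it is reported as an SAE, and it loses that status only if a later test is positive.

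On the COVID-19 side, SAP 5.7.3 says: "The number and percentage of participants with at least one molecularly confirmed SARS-CoV-2 infection will be tabulated by vaccine regimen". It also counts participants with a positive non-S ELISA, if that assay is available. Its narratives and symptom analyses cover confirmed cases, and the harm monitoring in SAP 5.7.2 counts molecularly confirmed cases.

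**The concern.** SAEs from first vaccination to the end of the study are a primary safety endpoint. The two documents use different criteria to decide which of them are counted: the preferred term in the SAP, and cause plus molecular confirmation in the protocol. A preferred term cannot show whether a test was positive, so the two rules cannot select the same events.

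What is at stake is the summary count of SAEs by regimen. An unconfirmed event can leave the SAE tables without entering any COVID-19 table. A complication of confirmed infection can stay in the SAE tables although the protocol would present it elsewhere.

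**Working it through.** The question is mainly where each type of event ends up, so the rules are set side by side.

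| Event | Protocol 9.4.2, 10.4.1 | SAP 5.6.1.2, 5.7.3 |
|---|---|---|
| SAE coded as suspected COVID-19, no positive molecular test | Stays in the SAE analysis | Out of the SAE tables; in a COVID-19 table only if N-ELISA positive, and then as a participant count; flagged in listings |
| Non-respiratory SAE caused by confirmed infection, listed term | Removed, presented separately | Out of the SAE tables; participant counted as infected; flagged in listings |
| Non-respiratory SAE caused by confirmed infection, term off the list | Removed, presented separately | Stays in the SAE tables |
| Respiratory infection, positive molecular test, any term | Not an SAE, or downgraded | Should not carry SAE status when the tables are made |

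Rows 1 and 3 are the mismatches. For row 3, acute renal dysfunction is an example: protocol 10.8.1 counts it among the criteria for severe COVID-19, and such an event could be coded to a renal term.

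Row 4 bears on what the list does. Respiratory infections with a positive test should already have lost SAE status, so any respiratory SAE still carrying a listed term should mostly be one without a positive test. Those are events that the protocol keeps.

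**Other AE tables.** SAP 5.6.1.1 limits the unsolicited AE tables to 28 days after each vaccination; only SAE tables cover the whole study. Within 28 days, a row 1 event may still appear in the tables of all events or of grade 3 and above, because the exclusion names only the SAE tables. The general remark that COVID-19 cases are analyzed separately leaves this unclear. After 28 days no other AE table applies. For Groups 1-5, each window covers the vaccination day plus 28 days:

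- days inside windows: 3 × 29 = 87
- scheduled days to the last visit: 393
- share outside: 1 − 87/393 = 0.779, about 78%, before any censoring at unblinding.

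**Size of one omitted event.** The protocol's Table 9 gives the one-sided 95% upper limit for zero events, 1 − 0.05^(1/N). This reproduces: N = 25, 11.29%; N = 50, 5.82%; N = 75, 3.92%; N = 150, 1.98%, against the stated 11.3%, 5.8%, 3.9% and 2.0%. For one event, the exact limit p solves (1 − p)^N + N·p·(1 − p)^(N−1) = 0.05:

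- N = 75: 6.17%, against 3.92% for zero events
- N = 25: 17.61%, against 11.29% for zero events.

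**Declaration.** SAP Appendix 2, on changes to the protocol-planned analyses, covers only the consequences of the study pause for Groups 7 and 8. The preferred-term rule is not there.

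**The case against.** The strongest reply is that nothing is concealed. The sentence that excludes the events from the tables also keeps them, flagged, in the SAE listings, and SAP 5.6.1.2 provides listings or narratives, as appropriate, for serious events and deaths. On listings the SAP shows more than the protocol, which removes confirmed cases from them as well. This stands. A reader might infer that SAEs are hidden or lost; the documents support only a gap in the summary tables.

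Second, the event may never occur. Protocol 8.1.2 calls for a swab at symptom onset and another on Day 3-8, and 10.4.5 asks for a diagnosis where possible, so a final code of suspected COVID-19 is a residual case. This also stands: the event can go untabulated, but it cannot be said that one will. The exposure terms matter less still, since nothing shows how exposure alone would meet the SAE criteria.

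Third, a reader might expect a confirmed COVID-19 pneumonia coded to a general pneumonia term to remain in the SAE tables. Protocol 10.4.1 already removes SAE status from such an event, so the reverse mismatch is limited to non-respiratory complications. A reader might also fear that thrombotic SAEs are dropped. No thrombotic term is on the list, so an event coded as thrombosis stays in the SAE tables.

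Fourth, SAP 5.6 plans frequencies and percentages and specifies no confidence limit for SAE rates. The shift from 6.2% to 3.9% is therefore an illustration, not a planned output that would change.

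None of this reconciles the two rules. The option to revise the term list does not help, because no list of terms can supply molecular confirmation.

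**Conclusion.** The conflict is real and undeclared. The SAP excludes by preferred term, including terms that need no positive test; the protocol excludes by cause and molecular confirmation. An unconfirmed SAE with a listed term can be absent from the SAE tables and from the COVID-19 tables, except as a participant count if N-ELISA positive. Beyond 28 days after a vaccination that gap is complete as far as AE tables are concerned. In the other direction, a non-respiratory SAE caused by confirmed infection but coded off the list is counted where the protocol says it should not be.

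Few events should be affected, and all remain in the listings. The illustration of 0/75 against 1/75 assumes that the omitted event is the group's only SAE. The point rests on the SAP being programmed as written, with the term list as the sole criterion. It deserves correction because it concerns the tabulation of a primary safety endpoint and costs very little to put right.

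**What to change.** In SAP 5.6.1.2:

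- Exclude an (S)AE from the tables only if it is judged to be caused by SARS-CoV-2 infection and that infection is molecularly confirmed. A positive test alone should not suffice: without the causal condition, an unrelated SAE in a PCR-positive participant, such as a thrombotic event, could leave the tables.
- Use the preferred-term list only to flag candidates for that decision, and keep unconfirmed listed-term SAEs in the SAE tables.
- State whether the exclusion also applies to the other AE tables.

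In SAP 5.7.3, add a table of the removed (S)AEs by regimen, so that they are presented separately as the protocol requires. Keep them flagged in the listings. Declare in Appendix 2 any departure from the protocol that remains, including the retention in listings.

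The cost is a few lines of SAP text, one table, and a link between AE records and molecular results. Protocol 8.1.2 and 8.1.3 already require positive RT-PCR results in the eCRF. The causal judgement is already implied by the protocol's rule; the SAP should say who makes it and that it is made before the tables are produced.
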